3.1 Intervention to be evaluated

Supervised PFMT plus vaginal pessary

The intervention being evaluated is an evidence-based supervised PFMT programme: 16 weeks duration (5 appointments, with a minimum of 3 face-to-face), with the addition of a vaginal pessary being fitted. In most cases PFMT will be supervised by a physiotherapist specialising in pelvic floor rehabilitation, and the pessary fitted by a healthcare professional specialising in gynaecology and pessary care. This may occur at the first PFMT appointment or at a follow-up pessary-fitting appointment soon after.

PEPPY protocol version 3.0 26/02/2025 ISRCTN: xxxxxx Page 15 of 51

Supervised PFMT

The control group will receive supervised PFMT, as described above. This is in line with the standard NHS patient care pathway recommended for women presenting with symptomatic prolapse which is a 16-week supervised programme of PFMT [18].

Further details about the intervention are provided in section 5.1.

4. TRIAL RECRUITMENT

4.1 Trial population

552 women ≥18 years who have been referred for PFMT for the treatment of prolapse of any stage will be randomised. NICE guidelines recommend that PFMT is considered for women with stage I and II prolapse [18], however in practice women with more severe prolapse at stage III are also referred for PFMT and are considered more likely to benefit from PFMT plus pessary (POGP survey) and therefore will be included.

4.2 Setting

Recruitment will take place in the context of hospital outpatient departments and community clinics where PFMT is delivered. Initial identification of potential participants will involve screening of clinic referrals and waiting lists for PFMT for prolapse.

4.3 Inclusion and exclusion criteria

Inclusion criteria:

We will include all women ≥18 years who have been referred for PFMT for prolapse of any severity, even if they have had previous prolapse treatment at any time (PFMT, pessary, surgery) as currently PFMT would be offered for all such women. If a woman has significant vaginal tissue atrophy, this will be treated according to the centre's usual practice, and will not be reason for exclusion or delay in randomisation.

Exclusion criteria:

We will exclude: women for whom prolapse is not the main presenting problem; women currently using a vaginal pessary (unless they discontinue for 1 month); women who are pregnant or less than 6 months' postnatal; women having active treatment for pelvic cancer; women with severe vulval disease; women who have cognitive impairment affecting capacity to give informed consent.

4.4 Identifying and approaching participants

Centre staff will identify women with prolapse referred for PFMT from referral letters and waiting lists and make contact with them prior to their first PFMT appointment to provide a Participant Information Leaflet, an invitation (Invitation 01) to consider taking part and an expression of interest form to return. Women who indicate they are interested will be screened for eligibility and have a participation discussion, prior to completing the consent form and baseline questionnaire.

All participants will have the option to complete the consent form and questionnaires electronically rather than completing a paper copy. A written record of the consent discussion, including discussion date, will be kept in the Eligibility CRF, and a copy filed in the medical records.

4.5 Non-recruited participants

The following anonymised information will be monitored and collected for all eligible women who choose not to take part:

- Year of birth
- Date of consultation when approached about the trial
- Reason for not participating if willing to give a reason

IRAS ID: 338183 PEPPY protocol version 3.0 26/02/2025 ISRCTN: xxxxxx Page 16 of 51

4.6 **Informed consent**

Dedicated staff members at each centre (appropriately trained and named on the delegation log) will make follow-up contact with women who indicated they would like to discuss the trial in full and carry out eligibility screening. They will obtain informed consent (written or e-consent) from those women who are eligible and willing (Main Trial, Consent Form 01). Paper consent forms will be checked, signed and dated. A copy of the consent/e-consent form will be held in the Site Investigator's File and the Trial Office's Trial Master File (TMF) and a copy will be given to the participant. Participants will complete a baseline questionnaire (postal or electronic as per the participant's preference).

Informed consent to participate in the trial will be sought and obtained according to Good Clinical Practice (GCP) guidelines. As part of the informed consent process, potential participants will be made aware of all aspects of the trial, including the potential risks and their responsibilities. There is no minimum time that potential participants should be given to decide whether to participate in the trial. Potential participants will be given enough time, and as long as they want, to accept or decline involvement and will be given opportunity to ask questions and to have these answered before giving consent.

It will be explained that entry into the trial is entirely voluntary, and that treatment and care will not be affected by their decision, and they can withdraw at any time. In the event of their withdrawal, it will be explained that their data collected to date cannot be erased and will be used in the final analyses.

Participants who cannot give informed consent (e.g. due to cognitive incapacity) will not be eligible for participation. Following informed consent, if a participant loses capacity, the consent given when capable remains legally valid. Identifiable data collected with consent will be retained and used in the study but no further data will be collected or research procedures carried out.

Participants who are not able to read or write (but who have capacity and can speak English sufficiently to understand the information being provided verbally) can agree to take part in the trial. In such cases, the trial team will provide them with written literature about the trial and read and discuss this information with the potential participant, if appropriate using interpreters provided by recruitment centres (where available). There should also be a discussion about the support networks that the participant has to facilitate their participation in the trial (for example help to complete questionnaires). If the potential participant is fully informed and wishes to take part in the trial, they will be asked to sign or make their mark on the consent form.

Within the consent form participants will be asked if they are willing to have an intervention appointment audio-recorded (yes/no) and if they are willing to hear more about being interviewed (yes/no) as part of the process evaluation. They will also be asked about being contacted in the future about this and (optionally) other relevant research.

Procedures to seek and gain informed consent from eligible potential participants are agreed and confirmed by Research Ethics Committees with responsibility for reviewing applications for research. The application for approval is made via the NHS Health Research Authority Research Ethics Service.

4.6.1 e-Consent

For participants who opt to consent using an e-consent form, they will do this via the secure web-based trial management system provided by CHaRT. If this option is preferred, participants will be asked to provide their email address which will be entered into the secure web-based trial management system. Participants will be sent a verification email with a link to verify their email. Once the email address is verified, participants will be automatically emailed the PIL (PIL 01) and a link to the participant e-consent form and baseline questionnaire for their unique study number. The e-consent form will be identical to the approved paper version of the consent form, with the approved PIL version number and date automatically populated. The participant will be

IRAS ID: 338183 PEPPY protocol version 3.0 26/02/2025 **ISRCTN: xxxxxx** Page 17 of 51 asked to provide their signature online via a signature box using a finger tracing via a touch screen or using a mouse.

Completed e-consent forms will be checked, and electronically counter-signed by someone listed on the delegation log with appropriate delegated responsibilities. The countersignature will only be recorded after discussion has taken place with the participant about the study and any questions have been answered. Only once both participant and person receiving consent signatures are present will informed consent be considered to have been obtained. Any econsent obtained will be verbally confirmed by the centre and the Trial Office before intervention commences. Participants will be sent a copy of the e-consent form for their own records and a copy will be retained in the investigator site file and TMF.

Should participants choose not to take part in the study their email address will be deleted from the trial management system after 3 months.

The trial management system used to record e-consent has a clear audit trail with tracking of all inserts or updates made. Database interactions are logged against a user and date/time and the audit trail can be downloaded and analysed at any time by authorised users.

Randomisation and allocation

When eligible consented participants attend their first PFMT appointment they will be randomised to one of the two groups using a secure web-based database and randomisation system developed and hosted by the Clinical Trials Unit (The Centre for Healthcare Randomised Trials (CHaRT) at the University of Aberdeen). Allocation will be minimised on age (<52/≥52 years), prolapse severity (POP-Q System: stage 0/1, stage 2, stage 3/4) and centre, ensuring balance between randomised groups in these factors. If a potentially eligible woman is identified in clinic prior to triage for PFMT (e.g. in a consultant gynaecology clinic appointment which involves vaginal examination), screening, consenting, randomisation could be triggered earlier.

Centre staff will make arrangements for each participant's follow-up PFMT appointments, and in addition a pessary fitting appointment, within 2 weeks, for participants randomised to PFMT plus pessary. Pessary fitting may occur at the first PFMT appointment, for example if the physiotherapist is trained in fitting pessaries, or if it is current practice to provide both services together.

4.8 Blinding

It is not possible to blind women or treating clinical staff to group allocation, however assessment of pelvic floor muscle function and prolapse severity at 12-month follow-up will be conducted by an assessor blinded to the participant's trial group. Participants will be requested in correspondence relating to their appointment not to disclose their group allocation to the blinded assessor, and the assessor will remind them of this at the start of the examination appointment. The assessor will be asked to record whether or not they were aware of group allocation prior to the assessment.

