A vaginal pessary will be fitted after the participant has completed the baseline questionnaire and been randomised (usually both will occur at the baseline/first PFMT appointment), in accordance with usual practice at the participating centre. There will be no restriction on pessary type, and women may be offered to self-manage their pessary if this option is available at their centre [21]. The type and size of pessary a woman uses will be recorded and reported. Pessary care will be delivered by a clinician (usually a gynaecologist, nurse or physiotherapist, depending on the service model at each centre) with specialist training in fitting and managing vaginal pessaries. Participants will be asked to use the pessary for at least 16 weeks (during the period of supervised PFMT) but can continue to use it if desired. Pessary review appointments will be offered to participants with the frequency dependent on whether they are self-managing or not. Participants who self-manage their pessary (who can remove the pessary themselves) will be asked to remove the pessary and those who do not self-manage will be asked to come to clinic to have the pessary removed 2 weeks before they receive their 6 and 12 month questionnaires. Participants will record details of their pessary use (insertion, removal, replacement, complications) in a diary (alongside their PFMT exercise recordings). Participants continuing pessary use after their time in the trial will receive care via their centre's usual pessary service.

An initial programme theory has been developed, proposing the pathway between intervention and outcome (Figure 1). The hypothesised mechanism of action is that successful pessary use will anatomically correct the prolapse. The anatomical correction will enable a more effective pelvic floor contraction which will lead to a greater improvement in prolapse symptoms than PFMT alone. Contextual factors suggested by previous evidence and theory to influence the pathway to outcome are included in the programme theory. Specifically, the outer circle signifies that intervention delivery, and outcomes are all influenced by context [22]. The nature of the

IRAS ID: 338183 PEPPY protocol version 3.0 26/02/2025 ISRCTN: xxxxxx Page 19 of 51

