6.2 Secondary outcome measures

Secondary outcomes include participant-reported pelvic floor dysfunction-related quality of life (QoL) measured using the Pelvic Floor Impact Questionnaire-7 (PFIQ-7) [23]. The PFIQ-7 was developed and validated in parallel with the PFDI-20 and includes questions on the effect of bladder (7 items), bowel (7 items) and prolapse (7 items) symptoms on activities, relationships and feelings. There are three subscales (UIQ-7, CRAIQ-7, POPIQ-7), with each sub-score ranging from 0-100, and the total score ranging from 0-300: higher scores reflect more impact on quality of life.

Other participant-reported secondary outcomes are general health-related QoL (EQ-5D-5L) (two-part instrument: five items on mobility, self-care, usual activities, pain/discomfort and anxiety/depression, plus the EQ-5D Visual Analogue Scale) [24]; Patient Global Impression of Improvement (PGI-I) (single-item participant rating of change in a condition since having treatment, validated for prolapse, with 7 responses from "very much better" to "very much

PEPPY protocol version 3.0 26/02/2025 **ISRCTN: xxxxxx** Page 20 of 51 worse") [25]; the ICIQ Vaginal Symptoms (ICIQ-VS) Sexual Matters subscale, with 4 items and score from 0 to 58, higher scores indicating worse sexual function [26]; uptake of other prolapse treatment (including surgery); self-efficacy for PFMT (Pelvic Floor Muscle Exercise Self-Efficacy Scale) [27]; and adherence to trial interventions (exercise/pessary use and experience diary).

An economic outcome, Quality Adjusted Life Years (QALYs), will be calculated from EQ-5D-5L data using the recommended tariff values [28].

Two clinical secondary outcomes are pelvic floor muscle strength and function (Modified Oxford Scale (MOS), 0 "no contraction" to 5 "strong (with lift) contraction", assessed via digital palpation) [29]; and prolapse severity (Pelvic Organ Prolapse Quantification (POP-Q) method, Stage I-IV) [20]. From our experience, use of the POP-Q system is challenging to implement in trials across many centres and different health professional groupings, therefore an experienced gynaecologist will be identified to undertake the POP-Qs at each centre.

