7.4 Follow-up

6 month follow-up

The 6 month questionnaire will be posted or emailed to participants for completion. Women using a pessary will be asked to pause pessary use 2 weeks before completion of this questionnaire. An appointment for pessary removal will be arranged if required.

12 month follow-up

The 12 month questionnaire will be posted or emailed to participants for completion. Women using a pessary will be asked to pause pessary use 2 weeks before completion of this questionnaire. An appointment for pessary removal will be arranged if required. Participants will attend a 12 month appointment for blinded assessment of pelvic floor muscle strength/function and prolapse severity.

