- Vaginal irritation/discomfort
- Granulation of vaginal tissue
- Involuntary expulsion of pessary
- Vaginal smell
- Vaginal discharge
- Vaginal infection
- Vaginal bleeding
- Psychological distress due to vaginal assessment (e.g. as a result of previous abuse or distressing labour)
- Pessary entrapment in the vagina requiring removal in theatre
- Urinary retention requiring catheterisation
- Faecal impaction requiring hospital intervention
- Fistula: recto-vaginal or vesico-vaginal
- Vaginal cancer
- Ureteric obstruction

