8.3 Procedures for detecting, evaluating, recording & reporting AEs and SAEs

8.3.1 Detecting AEs and SAEs

All AEs and SAEs meeting the criteria for recording within the PEPPY trial (see section 8.1) are recorded from the time a participant consents to join the trial until the last trial follow-up. The Trial Office and centre staff will ask about the occurrence of relevant AEs/SAEs (i.e. those that meet the criteria for recording within the PEPPY trial) at every appointment, within follow-up questionnaires, ad hoc phone calls and other contact with the participant.

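### The 12-month blinded examination is not shielded from adverse-event questioning, and allocation learned during it is not recorded

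*Protocol*

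**What the plan says.** Section 4.8 accepts that women and treating staff cannot be blinded, but states that "assessment of pelvic floor muscle function and prolapse severity at 12-month follow-up will be conducted by an assessor blinded to the participant's trial group". It gives two safeguards. Women are asked, in a letter sent beforehand, "not to disclose their group allocation to the blinded assessor, and the assessor will remind them of this at the start of the examination appointment". Then there is a single record of whether the blind held: "The assessor will be asked to record whether or not they were aware of group allocation prior to the assessment".

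Section 7.4 describes the visit: "Participants will attend a 12 month appointment for blinded assessment of pelvic floor muscle strength/function and prolapse severity". According to Table 2, both measures come from a vaginal examination in clinic.

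Section 8.3.1 makes the Trial Office and centre staff responsible for asking about relevant adverse events "at every appointment, within follow-up questionnaires, ad hoc phone calls and other contact with the participant", from consent to last follow-up. The expected events listed in Section 8.2 include "Involuntary expulsion of pessary" and, further down, entrapment of a pessary needing removal in theatre.

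Section 6.2 has pessary use paused for 2 weeks before the 12-month measurements. It says that failure to pause will be recorded and used in a sensitivity analysis.

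**The concern.** MOS and POP-Q at 12 months are the only outcomes that the protocol declares blinded. The primary PFDI-20 and the other participant-reported outcomes come from women who know their group. MOS is scored by digital palpation, so it involves judgement. It is also the blinded measure closest to the mechanism proposed in Section 5.1, a more effective pelvic floor contraction, and Section 9.1 makes a power claim for it.

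Two gaps meet at this visit. A woman may be asked about adverse events at the same appointment at which she has been told not to reveal her group, and an honest answer may name a pessary. The one item meant to show whether the blind held also stops before the examination, where further clues can arise. A leak at that stage would leave no trace. The report would then describe blinded results together with an awareness rate that looks better than the truth.

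**Working it through.** The point is textual. The one related figure in the plan is checked first.

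**The plan's MOS power claim (Section 9.1).** Inputs: 276 per group, 15% loss, two-sided 5% test, a 20-point difference in the proportion rated 2 or less. The intervention arm has at most 50% rated 2 or less, so take 50% against 70%.
- Evaluable per group: 276 × 0.85 = 234.6, assuming that the 15% loss also applies to clinic attendance.
- Null standard error, pooled proportion 0.60: √(2 × 0.60 × 0.40 / 234.6) = 0.0452.
- Alternative standard error: √((0.50 × 0.50 + 0.70 × 0.30) / 234.6) = 0.0443.
- Power: Φ((0.20 − 1.96 × 0.0452) / 0.0443) = 99.4%.

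The claim of more than 90% holds. The calculation assumes unbiased scoring, which the blind is there to protect.

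**When the assessor could learn the allocation, set against the rules.**
1. *At the visit, before the examination* (say, from an answer to an adverse-event question). The scores can be affected. The Section 4.8 item would record it.
2. *During the examination, before the scores are fixed* (a pessary not removed, or talk during the examination). The scores can be affected. The item would not record it. Its time limit could be read as applying to the assessor's awareness or to the act of recording, and on either reading this period is left out.
3. *After the scores are recorded.* The scores cannot be affected, so no record is needed.

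The item therefore covers the first period and misses the second.

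**Whether adverse-event questioning can fall in periods 1 or 2.** Section 8.3.1 covers every appointment up to last follow-up. Section 7.4 calls the blinded visit an appointment. Nothing in Sections 4.8, 7.4 or 8.3.1 says who asks at this visit or that asking follows scoring. Two of the sixteen events listed in Section 8.2 name the pessary. The protocol thus permits the questions to be put by the assessor before or during scoring, but does not require it.

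**What a leak could do, on assumed values only.** The documents give neither a rate of unblinding nor a size of scoring bias. Suppose no true effect, 50% rated 2 or less in both arms, and a net assessor-induced difference b across all evaluable women. Then SE = √(2 × 0.25 / 234.6) = 0.0462, and the false-positive rate is 1 − Φ(1.96 − b/SE) + Φ(−1.96 − b/SE):
- b = 2 points: b/SE = 0.43, rate about 7%
- b = 5 points: b/SE = 1.08, rate about 19%
- b = 10 points: b/SE = 2.17, rate about 58%

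This shows only how sensitive the MOS comparison is to a net shift. It is no estimate of the shift to expect.

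**The case against.** The case on the other side is substantial and limits the point in several ways.

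- A reader might infer that the protocol's own rules defeat the blind. They do not. Section 8.3.1 gives the questions to the Trial Office and centre staff and never names the assessor. Sections 4.8 and 8.3.1 can both be followed if a colleague asks, or if the questions come last. Site instructions or case report forms may already arrange this.
- A reader might infer from "an experienced gynaecologist will be identified to undertake the POP-Qs at each centre" and "Pessary care will be delivered by a clinician (usually a gynaecologist, nurse or physiotherapist" that the assessor may be the clinician who managed that woman's pessary. The overlap is one of profession only. Section 4.8 contrasts unblinded treating staff with a blinded assessor, and a clinician who had treated the woman could not meet that description. If it happened, it would be prior awareness, which the existing item records.
- A reader might infer that the item detects no unblinding at the visit. It does cover disclosure before the examination, and the assessor's reminder at the start is aimed at conversation.
- Discharge, irritation, bleeding and infection do not identify an arm. The protocol calls the expected events unlikely. Pessary use is paused beforehand. A pessary history does not prove allocation, since Section 4.3 admits previous users and Section 7.5 expects some women to receive the other treatment.
- A quantified bias is tempting. If 20–40% of assessments were unblinded and 10 points were shifted in each arm in opposite directions, the spurious difference would be 0.20 × 20 = 4 to 0.40 × 20 = 8 points. Every input is assumed, so this cannot be offered as a finding.
- A sensitivity analysis that excludes unblinded assessments may be in the statistical analysis plan, which is not shown. Its absence from the protocol is no fault.

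Two things remain after all of this. The protocol does not set the order or the owner of adverse-event questions at the blinded visit. The awareness item, whose timing the protocol itself fixes, leaves out the examination.

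**Conclusion.** The point holds as a gap in protection and in recording. The 12-month MOS and POP-Q assessments are not shielded from adverse-event questioning, and unblinding during the examination goes unrecorded, so the reported awareness rate can only err on the favourable side for that period. It concerns two secondary outcomes. The primary PFDI-20 analysis and the sample size of 552 do not depend on it. The documents give no basis for estimating how often the blind would leak or how far scores would move. The conclusion rests on the wording of Sections 4.8, 6.2, 7.4, 8.2 and 8.3.1, and on site-level documents not already closing the gap. A small amendment is justified because awareness that was never recorded cannot be recovered afterwards.

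**What to change.** 1. **Section 8.3.1:** state that at the 12-month blinded visit, questions about adverse events and pessary use are asked only after the MOS and POP-Q scores have been recorded, or by existing staff other than the assessor. Ascertainment need not suffer, since the questions are still asked and the questionnaire and telephone routes in that section remain.
2. **Section 4.8:** have the assessor complete the awareness item after the examination, stating whether they learned the allocation and, if so, whether this was before or during scoring.
3. **Optional, Section 4.8:** say outright that the assessor has not treated that woman. The word blinded already implies this, so it is a clarification only.

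The cost is one reworded case report form item, a sentence or two of protocol text, and slightly more coordination of the visit at small centres. No added visits or participants are needed. The change should be in place before the first 12-month assessments.
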